#### **2.7.4 Diabetes assessment**

Diabetes will be assessed by the analysis of:

- TEAEs
- change in glucose-related laboratory values over time
- shifts from baseline in glucose control category
- incidence of post-baseline new onset of diabetes.

Note that diabetes related tables dealing with the fasting glucose parameter will require the lab sample to be taken while fasting. Samples taken while the subject was not fasting will not be analyzed.

### 2.7.4.1 Diabetes TEAE

New onset/worsening of diabetes will be identified by the search criteria specified in [Appendix 5.2](#). The analysis will be performed for all subjects and then by baseline diabetes status. A subject will be identified as being diabetic at baseline if the targeted medical history notes that the subject is diabetic or the baseline HbA1c value is  $\geq 6.5\%$ .

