#### 2.7.4.4 Incidence of post-baseline new-onset of diabetes

The number of subjects who shift from no diabetes at baseline (defined as no medical history of diabetes in the targeted medical history CRF, HbA1c <6.5% at baseline, and fasting glucose <126 mg/dL at baseline (note that baseline is defined as the average of study entry and Day 1

fasting glucose values. If one fasting glucose value is missing (study entry or Day 1), the assessment will be based on the available data) to diabetes will be summarized. A 4-component definition of diabetes will be utilized. The 4 components are provided below.

1. Diabetic TEAEs identified by the search criteria in [Appendix 5.2](#), or
2. Post-baseline fasting glucose  $\geq 126$  mg/dL on two consecutive occasions, or
3. Initiation of anti-diabetic medication (ATC level 2 code: A10) at any time post-baseline, or
4. At least one post-baseline HbA1c  $\geq 6.5\%$ .

The number of subjects who have any of the 4 components (post-baseline new-onset of diabetes) will be summarized along with each component. This analysis will be performed for those subjects who have fasting glucose at baseline  $< 100$  mg/dL and then for those with fasting glucose at baseline  $\geq 100$  and  $< 126$  mg/dL.

The time to new-onset diabetes will also be summarized. Only subjects without diabetes at baseline will be included in the analysis. The time (weeks) to new-onset diabetes will be calculated from the date of the first administration of study drug.

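### SAP 2.7.4.1 and 2.7.4.4 define baseline diabetes differently, so diabetes TEAEs in one type of subject fall in the not-diabetic stratum of one summary and drop out of the other

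*SAP*

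**What the plan says.** SAP 2.7.4.1 (Diabetes TEAE) finds its events by search: "New onset/worsening of diabetes will be identified by the search criteria specified in" Appendix 5.2. On presentation it says: "The analysis will be performed for all subjects and then by baseline diabetes status". For that split a subject is "identified as being diabetic at baseline if the targeted medical history notes that the subject is diabetic or the baseline HbA1c value is" 6.5% or higher. Fasting glucose plays no part.

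SAP 2.7.4.4 (new-onset diabetes) counts subjects who move from no diabetes at baseline to diabetes. No diabetes at baseline is "defined as no medical history of diabetes in the targeted medical history CRF", together with "HbA1c <6.5% at baseline, and fasting glucose <126 mg/dL at baseline". The baseline glucose is the mean of the study-entry and Day 1 values, or the single value if one is missing. The first of four outcome components is "Diabetic TEAEs identified by the search criteria in" Appendix 5.2, the same search as in 2.7.4.1. For time to onset the section states: "Only subjects without diabetes at baseline will be included in the analysis". For the incidence summary it says "This analysis will be performed for those subjects who have fasting glucose at baseline" below 100 mg/dL, and then for those from 100 to below 126 mg/dL. There is no stratum at 126 mg/dL or above.

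**The concern.** The same search feeds two summaries that sit a few paragraphs apart, and each depends on who had diabetes at the start. A reader will expect the TEAE count among subjects not diabetic at baseline in 2.7.4.1 to match the TEAE component in 2.7.4.4. It need not, because the two sections draw the baseline line in different places.

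The difference looks unplanned. SAP 2.7.4.2 labels a baseline fasting glucose of 126 mg/dL or more as diabetes. SAP 2.7.4.3 does the same when both the study-entry and Day 1 values reach that level. Where the SAP drops a criterion on purpose it says so: 2.7.4.2 and 2.7.4.3 both state that they ignore medical history. SAP 2.7.4.1 makes no such statement about glucose.

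At stake is how the diabetes safety tables read. Subjects who start in the SAP's own diabetic glucose range are plausibly more likely than others to have a diabetes TEAE recorded. In 2.7.4.1 those events would sit among subjects shown as free of diabetes at baseline.

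**Working it through.** The plan gives no figure to reproduce. The check is to apply both rules to the same subjects.

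**Rules**
- 2.7.4.1: diabetic = history, or HbA1c ≥ 6.5%.
- 2.7.4.4: without diabetes = no history, and HbA1c < 6.5%, and fasting glucose < 126 mg/dL.

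**Cases**
Cross history (no, yes) with HbA1c (6.0%, 6.5%) and baseline fasting glucose (95, 110, 130 mg/dL): 2 × 2 × 3 = 12 profiles.

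| History | HbA1c | Fasting glucose (mg/dL) | Profiles | 2.7.4.1 | 2.7.4.4 |
|---|---|---|---|---|---|
| No | 6.0% | 95 | 1 | not diabetic | included, < 100 stratum |
| No | 6.0% | 110 | 1 | not diabetic | included, 100 to < 126 stratum |
| No | 6.0% | 130 | 1 | **not diabetic** | **excluded** |
| No | 6.5% | 95, 110 or 130 | 3 | diabetic | excluded |
| Yes | 6.0% or 6.5% | 95, 110 or 130 | 6 | diabetic | excluded |

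The rules agree on 11 of 12 profiles. The one disagreement is no history, HbA1c below 6.5% and fasting glucose at or above 126 mg/dL. It runs one way: nobody diabetic under 2.7.4.1 enters the 2.7.4.4 set.

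The mean decides who is affected. Readings of 140 and 115 give (140 + 115)/2 = 127.5, so the subject is excluded from 2.7.4.4. Readings of 120 and 130 give (120 + 130)/2 = 125, so the subject is included.

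**Size, on assumptions only**
The documents give none of these inputs. Assume 200 Group 1 subjects with no history and HbA1c below 6.5%. Let a fraction f of 1% to 5% have fasting glucose of at least 126 mg/dL, with a diabetes TEAE risk h of 30% to 50%, and let the rest have a risk of 8%. The not-diabetic rate in 2.7.4.1 is then R = f × h + (1 − f) × 0.08.
- Low end: 0.01 × 0.30 + 0.99 × 0.08 = 0.0030 + 0.0792 = 0.0822. Against 0.080 that is a ratio of 1.03. The 2 affected subjects contribute 2 × 0.30 = 0.6 expected events.
- High end: 0.05 × 0.50 + 0.95 × 0.08 = 0.025 + 0.076 = 0.101, a ratio of 1.26. The 10 affected subjects contribute 10 × 0.50 = 5 expected events.

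**The case against.** There is a real case for leaving 2.7.4.1 as it is.

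- **Protocol.** Section 8.2.4.2 has sites report new onset in subjects without a history of diabetes, and worsening in those with a history, which it ties to baseline HbA1c of at least 6.5%. Baseline fasting glucose is not used. SAP 2.7.4.1 is therefore the closer of the two to the rule under which the events were reported. This stands, and it means that the fix has a cost.
- **Function.** One outcome component of 2.7.4.4 is two consecutive post-baseline fasting glucose values of 126 mg/dL or more, so subjects already at that level have to be removed. SAP 2.7.4.1 has only TEAEs as its outcome and no such need. The reason is plausible, but the SAP does not state it, and it does not explain why pre-existing diabetic-range glucose should be shown as no diabetes at baseline.
- **Traceability.** Both definitions are explicit and the listings carry all AEs, so the affected subjects can be found. This also stands. A reader might infer that the two counts can never be reconciled, but they can, with extra work that the tables do not prompt.

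A reader might also infer that 2.7.4.1 misclassifies these events as new onset. It does not: it tabulates new onset and worsening together and labels no single event as either. The new-onset reading comes only from the stratum in which the event lands.

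**Conclusion.** The inconsistency is real and unexplained, and it is minor. It affects one type of subject, in one direction, in descriptive safety summaries. The all-subjects diabetes TEAE table and the primary endpoint are unaffected.

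It is tempting to conclude that the not-diabetic TEAE rate is materially inflated. The documents do not support that. The relative difference of 3% to 26% comes entirely from assumed inputs. The upper figure needs the highest prevalence and the highest risk together, and the lower one is 0.2 percentage points. The number of affected subjects is not given and may be small. The disagreement between the definitions depends on none of these assumptions.

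**What to change.** Derive one baseline-diabetes flag and use it both for the strata in SAP 2.7.4.1 and for the at-risk set in 2.7.4.4. A subject is diabetic at baseline if any of these holds:
- the targeted medical history is positive;
- baseline HbA1c is at least 6.5%;
- baseline fasting glucose, derived as in 2.7.4.4, is at least 126 mg/dL.

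State how a subject with no valid baseline fasting glucose is classified. SAP 2.7.4 drops non-fasting samples, and 2.7.4.4 covers one missing value but not two. Without a rule, such a subject could count as not diabetic in 2.7.4.1 and still fall in neither glucose stratum of 2.7.4.4.

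The cost is a clause of SAP text and one shared variable. No new data are needed, because serum glucose is scheduled at study entry and Day 1 in Protocol Tables 6-1 and 6-2. The small downside is that the 2.7.4.1 strata then depart from Protocol 8.2.4.2. Record this in SAP section 4, which now reports no change from the protocol, and footnote the number of subjects whose status differs between the two rules.

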### 2.7.4.2 Change in glucose-related laboratory values over time

This analysis only utilizes laboratory data (fasting glucose and HbA1c). The change from baseline to the last observation and the worst observation will be summarized separately for fasting glucose and HbA1c overall and then by baseline glucose control status. Baseline glucose control status will be identified separately for fasting glucose and HbA1c using the values provided in the table below (note that medical history will not be taken into account for this analysis). Figures will also be created showing mean fasting glucose and HbA1c values over time by baseline glucose control status.

Parameter	Baseline Glucose Control Status	Baseline Laboratory Values
Fasting Glucose*	Normal	<100 mg/dL
	Impaired	$\geq 100$ to <126 mg/dL
	Diabetes	$\geq 126$ mg/dL
HbA1c**	Normal	<5.7%
	Impaired	$\geq 5.7$ to <6.5%
	Diabetes	$\geq 6.5\%$

\* Baseline uses average of ORION-3 study entry and Day 1 fasting glucose values. If one fasting glucose value is missing, the assessment will be based on the available data.

\*\* ORION-3 Day 1 assessment will be considered as baseline for HbA1c. If missing, then the baseline will be based on assessment at ORION-3 study entry.

### 2.7.4.3 Shifts from baseline in glucose control category

Shifts from baseline in glucose control category will be summarized two different ways: the change from ORION-3 baseline to the worst and then again for the change to last glucose control category. Note that medical history will not be taken into account for this analysis. If consecutive fasting glucose measurements fall in two separate categories, or if only one pre- or post-baseline fasting glucose measurement is available, then the classification will be based on the HbA1c measurements only. If HbA1c is missing then both consecutive fasting glucose measurements must fall in a category otherwise the lower category will be used.

Shift Category*	Baseline Values**	Post-baseline Values
Normal to Normal (no change)	Fasting glucose < 100 mg/dL on ORION-3 study entry or Day 1 AND HbA1c < 5.7%	Fasting glucose < 100 mg/dL on two consecutive occasions AND HbA1c < 5.7%

Normal to Impaired	Fasting glucose < 100 mg/dL on ORION-3 study entry or Day 1 AND HbA1c < 5.7%	Fasting glucose ≥ 100 and < 126 mg/dL on two consecutive occasions OR HbA1c ≥ 5.7 and < 6.5%
Normal to Diabetes	Fasting glucose < 100 mg/dL on ORION-3 study entry or Day 1 AND HbA1c < 5.7%	Fasting glucose ≥ 126 mg/dL on two consecutive occasions OR HbA1c ≥ 6.5%
Impaired to Normal	Fasting glucose ≥ 100 and < 126 mg/dL on ORION-3 study entry and Day 1 OR HbA1c ≥ 5.7 and < 6.5%	Fasting glucose < 100 mg/dL on two consecutive occasions AND HbA1c < 5.7%
Impaired to Impaired (no change)	Fasting glucose ≥ 100 and < 126 mg/dL on ORION-3 study entry and Day 1 OR HbA1c ≥ 5.7 and < 6.5%	Fasting glucose ≥ 100 and < 126 mg/dL on two consecutive occasions OR HbA1c ≥ 5.7 and < 6.5%
Impaired to Diabetes	Fasting glucose ≥ 100 and < 126 mg/dL on ORION-3 study entry and Day 1 OR HbA1c ≥ 5.7 and < 6.5%	Fasting glucose ≥ 126 mg/dL on two consecutive occasions OR HbA1c ≥ 6.5%
Diabetes to Normal	Fasting glucose ≥ 126 mg/dL on ORION-3 study entry and Day 1 OR HbA1c ≥ 6.5%	Fasting glucose < 100 mg/dL on two consecutive occasions AND HbA1c < 5.7%
Diabetes to Impaired	Fasting glucose ≥ 126 mg/dL on ORION-3 study entry and Day 1 OR HbA1c ≥ 6.5%	Fasting glucose ≥ 100 and < 126 mg/dL on two consecutive occasions OR HbA1c ≥ 5.7 and < 6.5%
Diabetes to Diabetes (no change)	Fasting glucose ≥ 126 mg/dL on ORION-3 study entry and Day 1 OR HbA1c ≥ 6.5%	Fasting glucose ≥ 126 mg/dL on two consecutive occasions OR HbA1c ≥ 6.5%

\*No change (Normal to Normal, Impaired to Impaired, and Diabetes to Diabetes), Worsened (Normal to Impaired, Normal to Diabetes, and Impaired to Diabetes), and Improved (Impaired to Normal, Diabetes to Impaired, and Diabetes to Normal) categories will also be summarized.

\*\* If one fasting glucose value is missing (ORION-3 study entry or Day 1), the assessment will be based on the available data.

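### SAP 2.7.4.3 can class a fasting glucose pair as Normal although both values are abnormal, when the pair straddles 126 mg/dL and HbA1c is below 5.7%

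*SAP*

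**What the plan says.** SAP 2.7.4.3 places each subject in Normal, Impaired or Diabetes at baseline and after baseline, and tabulates the shift to the worst and to the last category. The post-baseline definitions in its table (HbA1c in per cent) are:

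- Normal: "Fasting glucose < 100 mg/dL on two consecutive occasions AND HbA1c < 5.7"
- Impaired: "Fasting glucose ≥ 100 and < 126 mg/dL on two consecutive occasions OR HbA1c ≥ 5.7 and < 6.5"
- Diabetes: "Fasting glucose ≥ 126 mg/dL on two consecutive occasions OR HbA1c ≥ 6.5"

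Baseline Impaired has the same form, using study entry and Day 1: "Fasting glucose ≥ 100 and < 126 mg/dL on ORION-3 study entry and Day 1 OR HbA1c ≥ 5.7 and < 6.5". A table footnote counts Impaired to Normal as Improved.

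A text rule above the table deals with pairs that disagree: "If consecutive fasting glucose measurements fall in two separate categories". It also covers a subject who has just a single glucose value before or after baseline. Both situations have the same outcome: "then the classification will be based on the HbA1c measurements only". A further rule deals with absent HbA1c results: "If HbA1c is missing then both consecutive fasting glucose measurements must fall in a category otherwise the lower category will be used".

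**The concern.** A disagreement between two glucose values can mean two different things. In 98/102 one value is normal, and letting HbA1c decide is reasonable. In 124/128 neither value is normal, and the only open question is whether the subject is Impaired or Diabetes. The text rule treats both pairs alike, so an HbA1c below 5.7% takes the second pair to a category that neither glucose value supports.

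The shift table is one of four planned diabetes assessments in SAP 2.7.4, and long-term safety is a secondary objective. The rule breaks down around 126 mg/dL, which is where movement from Impaired towards Diabetes would appear.

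**Working it through.** **Rule applied literally.** A concordant pair is combined with HbA1c by the table's AND/OR logic, taking the higher category. A discordant pair follows HbA1c. If HbA1c is missing, the lower glucose category applies. An HbA1c of 5.5% is used for illustration.

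| Glucose pair (mg/dL) | HbA1c | SAP class | Row met in the table |
|---|---|---|---|
| 110/112 | 5.5% | Impaired | Impaired |
| 124/125 | 5.5% | Impaired | Impaired |
| 124/128 | 5.5% | Normal | none |
| 128/130 | 5.5% | Diabetes | Diabetes |
| 124/128 | missing | Impaired | none |
| 124/128 | 5.8% | Impaired | Impaired |
| 124/128 | 6.6% | Diabetes | Diabetes |

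Three inconsistencies follow.

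1. The class is not ordered in glucose: it runs Impaired, Normal, Diabetes as glucose rises.
2. A normal HbA1c overrides 124/128 but does not override the lower pair 110/112.
3. Only the text rule makes 124/128 Normal; the table's Normal row excludes it.

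**Effect on the shift labels (HbA1c 5.5% throughout).**

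- Baseline 110/112, later 124/128: Impaired to Normal, counted as Improved although both values rose.
- Normal baseline, later 124/128: No change.
- Baseline 124/128, later 124/125: Normal to Impaired, counted as Worsened although the second value fell. For the same baseline pair, SAP 2.7.4.2 averages (124 + 128)/2 = 126 mg/dL and calls it Diabetes.

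**Size for one pair.** The documents give no within-subject variability. Assume independent normal glucose values with SD 6-10 mg/dL and HbA1c always below 5.7%. Let n, i and d be the probabilities that one value is below 100, from 100 to below 126, and 126 or above. Under the SAP rule P(Normal) = 1 − i² − d². Under the lower-category rule it is 1 − (1 − n)².

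| True level | SD | n | i | d | SAP P(Normal) | Lower-category P(Normal) |
|---|---|---|---|---|---|---|
| 124 | 6 | 0.0000 | 0.631 | 0.369 | 0.47 | 0.000 |
| 124 | 8 | 0.0013 | 0.597 | 0.401 | 0.48 | 0.003 |
| 124 | 10 | 0.0082 | 0.571 | 0.421 | 0.50 | 0.016 |
| 112 | 8 | 0.0668 | 0.893 | 0.040 | 0.20 | 0.13 |

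At SD 8 a true rise from 112 to 124 mg/dL raises P(Normal) from 0.20 to 0.48. Under the lower-category rule it falls from 0.13 to 0.003.

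**Size for the worst category.** Protocol 7.1.6 schedules post-baseline fasting glucose with HbA1c at Days 270, 540, 810, 1080, 1350 and EOS: six values, hence five consecutive pairs. The worst category is Normal only if no adjacent pair is both Impaired or both Diabetes. At a true level of 124 almost no value falls below 100, so the values must alternate, with probability about 2(i·d)³. At SD 8 this is 2 × (0.597 × 0.401)³ = 0.027. Adding the rare sequences with a value below 100 gives 0.028. Over SD 6, 8 and 10 the result is 0.025, 0.028 and 0.033.

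**The two tables compared.** For a true rise from 112 to 124 mg/dL at SD 8, P(baseline Impaired) = 0.893² = 0.80. The Impaired-to-Normal shift then has probability 0.80 × 0.48 = 0.38 in the last-category table and 0.80 × 0.028 = 0.02 in the worst-category table.

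**What the proposed rule changes.** A pair with one value below 100 has Normal as its lower category, so HbA1c still decides. An Impaired/Diabetes pair with HbA1c of 5.7% or more, or missing, keeps its present class. Only an Impaired/Diabetes pair with HbA1c below 5.7% moves, from Normal to Impaired.

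**The case against.** HbA1c as a prespecified tie-breaker is defensible when two glucose values disagree. That stands for pairs with one normal value, and the proposed rule leaves them alone. It does not cover a pair with no normal value.

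The table can be said to govern over the text, so that 124/128 is never Normal. But the pair with HbA1c 5.5% meets no post-baseline row, so a programmer must use the text rule. The two need reconciling on either view.

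Other outputs protect the safety signal, and this stands. SAP 2.7.4.2 reports continuous change to the last and worst values. SAP 2.7.3 has a separate laboratory shift analysis, and 2.7.4.1 covers adverse events. The new-onset diabetes analysis in 2.7.4.4 does not use this rule. A reader might infer that the plan would miss new diabetes; the documents do not support that.

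A reader might also infer that the rule systematically favours inclisiran. That is not supported either, because a discordant baseline classed Normal pushes later results towards Worsened.

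Finally, 47-50% might be read as the share of subjects misclassified. It is the probability for one pair at one true level, with HbA1c held below 5.7%. The documents do not say how often that combination occurs.

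**Conclusion.** The point holds: as written, the text rule yields a category that contradicts the SAP's own table and its own rule for missing HbA1c, and it can report rising glucose as improvement. It applies only when one value is 100 to below 126 mg/dL, the other is 126 or above, and HbA1c is available and below 5.7%.

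The last-category table and the baseline class are the most exposed, because each rests on one pair: about 47-50% Normal at a true level of 124 mg/dL under the stated assumptions. The worst-category table is largely protected by repeated pairs, at about 2.5-3.3%. Those figures rest on an assumed SD, independent values and a fixed normal HbA1c. The net direction of bias and the number of subjects affected cannot be determined from the documents. The outputs are descriptive with no test attached, so this should be corrected but does not threaten the trial's main conclusions.

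**What to change.** Replace the text rule for discordant pairs in SAP 2.7.4.3 with: *If two consecutive fasting glucose values fall in different categories, the glucose category is the lower of the two, and it is then combined with HbA1c as for a concordant pair.* State that it applies to baseline and post-baseline pairs. It extends the SAP's existing rule for missing HbA1c, and Diabetes on glucose still needs two values of 126 mg/dL or more.

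In the same edit, reconcile the handling of a single glucose value. The text sends it to HbA1c alone, whereas the table footnote says that a missing study-entry or Day 1 value leaves the assessment to whatever data are available. With one baseline value of 130 mg/dL and HbA1c 5.5%, the text gives Normal, while the footnote can be read as giving Diabetes.

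The cost is a short change to the SAP wording and the derivation code, with no new data. Slightly more subjects will be shown as Impaired. A baseline of 124/128 would still be Impaired here and Diabetes under the averaging in 2.7.4.2, so a table note on the two definitions would help.

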#### 2.7.4.4 Incidence of post-baseline new-onset of diabetes

The number of subjects who shift from no diabetes at baseline (defined as no medical history of diabetes in the targeted medical history CRF, HbA1c <6.5% at baseline, and fasting glucose <126 mg/dL at baseline (note that baseline is defined as the average of study entry and Day 1

fasting glucose values. If one fasting glucose value is missing (study entry or Day 1), the assessment will be based on the available data) to diabetes will be summarized. A 4-component definition of diabetes will be utilized. The 4 components are provided below.

1. Diabetic TEAEs identified by the search criteria in [Appendix 5.2](#), or
2. Post-baseline fasting glucose  $\geq 126$  mg/dL on two consecutive occasions, or
3. Initiation of anti-diabetic medication (ATC level 2 code: A10) at any time post-baseline, or
4. At least one post-baseline HbA1c  $\geq 6.5\%$ .

The number of subjects who have any of the 4 components (post-baseline new-onset of diabetes) will be summarized along with each component. This analysis will be performed for those subjects who have fasting glucose at baseline  $< 100$  mg/dL and then for those with fasting glucose at baseline  $\geq 100$  and  $< 126$  mg/dL.

The time to new-onset diabetes will also be summarized. Only subjects without diabetes at baseline will be included in the analysis. The time (weeks) to new-onset diabetes will be calculated from the date of the first administration of study drug.

